Success Criteria:	All subjects follow research protocol as summarized in Error! Reference source not found. and Error! Reference source not found. Follow-up at 1 year post-crossover completion with ≥80% of the participants.
Rationale:	Overall randomization and study design has been approved by NIH staff. As this is a deviation from what was originally in the proposal, this new study design should be followed. All further deviations should be negotiated and approved by NIH prior to changes being made.
Milestone 3.6:	Review IRB and IDE paperwork to ensure both are up to date and allow for a sufficient scope and number of subjects for successful completion of work proposed in the upcoming year.
Success Criteria:	Confirm paperwork is up to date and NINDS staff has the most recent version.
Rationale:	Maintaining IRB and IDE approval is a requirement for a clinical study.

Year 4

Milestone 4.1:	Maintain active membership status in NIH-coordinated data sharing consortium.
Success Criteria:	Actively participate in the data sharing consortium, and adopt best practices/efforts to comply with the recommendations of the data sharing consortium, throughout all years and/or stages of the award.
Rationale:	Participation and maintaining an active membership status in the consortium is a requirement of the RFA.
Milestone 4.2:	Complete the pre-operative assessment battery and implant the Boston Scientific Vercise DBS system with the directional lead in at least 3 additional participants in Y4, for a total of at least 30 enrolled and implanted participants.
Success Criteria:	Successfully implant the Vercise DBS system with directional lead, extension cable, and pulse generator in 3 participants using standard STN stereotaxy. Successful implant is defined as placement of the entire DBS system without surgical adverse events (such as stroke, infection, seizure) or any other adverse event that prevents postoperative device activation, adjustment,

and/or behavioral testing. Depending on potential attrition and AEs, this modest recruitment goal for early Y4 will provide flexibility to recruit additional participants to reach our goal of 30 participants for randomization, if necessary. Results will be recorded in a surgical implantation document including system tests showing normal DBS electrode impedances and side effect and efficacy thresholds during test stimulation. These data will be provided to NIH. To maintain blinding, patients will not be told which survey is being performed or which treatment condition they will receive.

Rationale: This is a minimum requirement to reach target of 30 participants implanted and randomized in the crossover by the end of Year 4 and will enable initial follow-up to be completed by Year 5.

Milestone 4.3: **Demonstrate changes in the therapeutic window using directional DBS and field shaping, guided by cortical activation patterns elicited by DBS during surgery (SAs 1.1, 1.2, 2.1, and 2.2).**

Success Criteria: Guided by cortical physiology elicited by DBS, demonstrate $\geq 20\%$ increase in therapeutic window in at least one grouping of 3 contact segments versus omnidirectional DBS in $\geq 40\%$ of the participants who have completed the field shaping survey by the end of Year 4. As per Milestone 2.4, we will classify all stimulation side effects by type (i.e., motor, sensory, oculomotor, ataxia, autonomic, etc.). The field shaping survey will be performed in conjunction with the assessment battery after the second treatment phase. To maintain blinding, patients will not be told which survey is being performed or which treatment condition they will receive.

Rationale: The Field shaping survey will evaluate the feasibility of using ECoG/EEG biomarkers to guide directional DBS activation and initiate the final crossover condition. This is a unique dataset that will link simultaneous EEG/ECoG activity elicited by directional DBS with the behavioral response to stimulation.

Milestone 4.4: **Safety Monitoring Committee will meet to discuss all AEs and SAEs at the end of Year 4.** This committee will also meet on an as-needed basis following SAEs to determine whether they are potentially study-related versus a known complication of DBS surgery.

Success Criteria: Meeting proceedings and decisions will be communicated to the PI and NINDS program officers.

Rationale: This process will ensure ongoing safety of the study.

Milestone 4.5: **Participant enrollment follows approved protocol.**

Success Criteria: All subjects follow research protocol as summarized in **Error! Reference source not found.** and **Error! Reference source not found.** Follow-up at 1 year post-crossover completion with $\geq 80\%$ of the participants.

Rationale: Overall randomization and study design has been approved by NIH staff. As this is a deviation from what was originally in the proposal, this new study design should be followed. All further deviations should be negotiated and approved by NIH prior to changes being made.

Milestone 4.6: **Hold a Scientific Steering Group meeting to review project status, problems and direction.**

Success Criteria: Meeting participants, proceedings and decision(s) will be communicated to NIH program staff.

Rationale: This is a requirement of the RFA and will help to ensure continued progress and success of the project.

Milestone 4.7: **Review IRB and IDE paperwork to ensure both are up to date and allow for a sufficient scope and number of subjects for successful completion of work proposed in the upcoming year.**

Success Criteria: Confirm paperwork is up to date and NINDS staff has the most recent version.

Rationale: Maintaining IRB and IDE approval is a requirement for a clinical study.

Year 5

Milestone 5.1: **Maintain active membership status in NIH-coordinated data sharing consortium.**

Success Criteria: Actively participate in the data sharing consortium, and adopt best practices/efforts to comply with the recommendations of the data sharing consortium, throughout all years and/or stages of the award.

Rationale: Participation and maintaining an active membership status in the consortium is a requirement of the RFA.

Milestone 5.2: **Participant enrollment follows approved protocol.**

Success Criteria: All subjects follow research protocol as summarized in **Error! Reference source not found.** and **Error! Reference source not found.** Follow-up at 1 year post-crossover completion with ≥80% of the participants.

Rationale: Overall randomization and study design has been approved by NIH staff. As this is a deviation from what was originally in the proposal, this new study design should be followed. All further deviations should be negotiated and approved by NIH prior to changes being made.

Milestone 5.3: **Hold a Scientific Steering Group meeting to review project status, problems and direction.**

Noninvasive Biomarkers to Advance Emerging DBS Electrode Technologies in Parkinson's Disease
(SUNDIAL, SUBthalamic Nucleus DIrectionAL vs Circular Stimulation Study)

NCT03353688

11/30/2023

Statistical Analyses. Each patient participates in all sub-Aims, therefore overall sample size is determined by the sub-Aim requiring the largest sample.

SA1. To test the hypothesis that specific contacts on a novel segmented DBS lead in the STN region activate functionally distinct populations of cortical axons within individual PD patients. SA1.1 will measure within-participant contrasts in therapeutic window and UPDRS part 3 change versus pre-op baseline across the different segments on the directional DBS lead with two-way repeated measures mixed models using Proc Mixed in SAS, with conventional versus current steering DBS contacts as factors and therapeutic window and change in UPDRS part 3 as data. The primary outcome measure for SA1.2 will compare whether intraoperative ERPs predict within-participant changes in the clinical outcomes from SA1.1. We will contrast the ERPs within and across stimulation sites with two-way repeated measures mixed models using Proc Mixed in SAS, with stimulus amplitude, location, and recording modality (EEG or ECOG) as factors and P1/N1 latency and HFO integrated area as data. Using linear contrasts from the regressions, we will directly compare whether EEG and ECOG measures of DBS amplitude thresholds (1) that change P1/N1 latency and (2) elicit the large amplitude HFOs better predict the size of the therapeutic window for a given DBS electrode contact. Secondary outcomes will correlate these amplitude thresholds with changes in the UPDRS part 3 score, UPDRS subscores, and other elements of the Motor battery measured in SA1.1. To control for potential subclinical corticospinal tract activation, we will report the latency and magnitude of EMG response(s) in the contralateral arm and leg muscles using residual analyses, when and if these responses are present. Sample size for SA1. Our preliminary findings show robust within- and between-subject changes in ERP latency that predict postoperative motor side effects. For the first primary outcome, a sample size of 18 will have 80% power to detect a difference between a null hypothesis regression slope of 0 and an alternative regression slope of 0.3 or higher standardized units, assuming that the standard deviation of the predictor variable, DBS amplitude threshold, is 2.370 mA (the standard deviation of the stimulus intensities) and the standard deviation of the normalized residuals ($sd=1$) of the therapeutic window using a t-test with a 0.05 two-sided significance level. Thus, we will be overpowered for SA1, because a large sample of 30 is dictated by SA2.3. As an additional secondary analysis, we will compare the predictive power of EEG versus ECOG, we will first regress the primary outcomes on EEG and then determine how much of the residual variance is explained by ECOG. If EEG explains 50% of the variance in the primary outcome, then we will have 80% power to detect an increase in the R-square of 8.6%. If the additive R-square of EEG is 25%, we will have 80% power to detect an increase of 12.9%. If we cannot demonstrate superiority of ECOG, we would default to the less invasive modality. We will look at the assumptions of the model by examining the residual plots in the regression models for both modalities.

SA2. To test the hypothesis that patient-specific combinations of active contacts on the segmented DBS lead, selected based upon behavioral versus ERP criteria, improve the efficacy and tolerability of DBS therapy. SAs 2.1 and 2.2 occur on the same day in an acute safety, feasibility, and dose-finding study to inform stimulation parameters for current steering in the double-blind, randomized crossover study in SA 2.3. For SAs 2.1 and 2.2, we will use two-way repeated measures linear mixed models using Proc Mixed in SAS to contrast (1) conventional DBS (as though the lead does not have current steering), (2) combinations of active contacts selected by behavior alone, and (3) combinations of active contacts

selected based cortical ERP physiology, using both therapeutic window and change in UPDRS part 3 as data nested within person. Secondary analyses will contrast the efficacy of these DBS adjustment strategies based upon changes in other elements of the Motor battery. In SA 2.3, we use the randomized, doubleblind crossover trial to compare changes in UPDRS and other measures of quality of life and motor, cognitive, behavioral, and speech function across the DBS programming strategies identified in SA 2.1. The primary statistical analysis will use Proc Mixed in SAS with active contact groupings including (1) conventional DBS, (2) multiple active contacts selected based on behavior, and (3) multiple active contacts based on ERPs as factor and patient preference and changes in PDQ-39 and UPDRS part 3 as data. Sample size for SA2. We will obtain multiple repeated measures within participants and can readily detect changes in patient preference, PDQ-39, UPDRS part 3, and other motor and non-motor variables of interest. Patient reported evidence for the hypothesis of superiority of current steering will be shown by determining that 20 or more of the 30 participants favor either current steering approach over conventional DBS using a binomial distribution based on patient preference (vote), PDQ-39, and UPDRS part 3. This would achieve a p value of < 0.049 . We will declare current steering DBS to be clinically superior to conventional therapy based on patient preference if 20 or more patients meet this criterion. We will measure the frequency by which current steering provides better outcomes versus conventional DBS, which could still be highly relevant and significant clinically (even if preferred by <20 participants). Secondary measures will quantify within-participant changes in upper limb dexterity, gait speed test, posture and balance, cognitive/behavioral measures, speech, and motor diaries. Additionally, we will contrast the probability that active contacts are shared among the programming strategies (conventional DBS, current steering guided by behavior, and current steering guided by cortical physiology). The extent to which contacts and stimulation parameters are shared among these approaches could be informative and provide a useful internal validation of the current steering approach.

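### SA1.2 asks whether ERPs predict the therapeutic window within a patient, but neither its stated mixed model nor its powered regression separates within-patient from between-patient association

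*SAP*

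**What the plan says.** All of this is in the SAP, Statistical Analyses, SA1, unless noted.

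- **Question.** SA1.2 is to establish "whether intraoperative ERPs predict within-participant changes in the clinical outcomes from SA1.1". The protocol gives the same within-participant aim for SA 1.2 (Item 23, Milestone 2.5, rationale).
- **Mixed model.** The one model written for SA1.2 is a repeated measures mixed model "with stimulus amplitude, location, and recording modality (EEG or ECOG) as factors and P1/N1 latency and HFO integrated area as data". The SA1.1 sentence also uses the word data for the response, so here the ERP measures are the response.
- **Prediction step.** Linear contrasts from regressions are to show whether EEG or ECoG amplitude thresholds "better predict the size of the therapeutic window for a given DBS electrode contact". No patient term, random effect or centring is given.
- **Power.** The statement for the first of the SA1 primary outcomes reads: "a sample size of 18 will have 80% power to detect a difference between a null hypothesis regression slope of 0". The slope to be detected is put at 0.3 in standardized units. It is assumed that "the standard deviation of the predictor variable, DBS amplitude threshold, is 2.370 mA", with unit residual SD for the window. The 18 is then compared with the 30 participants that SA2.3 requires.
- **Contrast.** For SA2.1 and SA2.2 the SAP does say that the data are nested in the person. The SA1.2 regression has no such statement.

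**The concern.** Choosing a contact is a within-patient decision: among the segments on this patient's lead, which has the wider window? A model with ERP latency or HFO area as response shows how ERPs vary with amplitude, site and recording modality. It holds no clinical outcome, so no contrast from it can show that ERPs predict the window.

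That leaves the regression of window on threshold. Without a patient effect or a split of the predictor, its slope mixes two associations. One is between patients: for example, a lead lying closer to the capsule might have low thresholds and narrow windows on every contact (a hypothetical mechanism, used only to illustrate). The other is within patients. Only the second helps to choose a contact. A positive SA1.2 result could come from the first alone, and a real within-patient signal could be missed if the data were reduced to one value per patient.

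**Working it through.** **1. The plan's own figure.** Inputs from the SAP, Sample size for SA1: slope 0.3, predictor SD 2.370 mA, residual SD 1, two-sided alpha 0.05, t-test. For a simple regression slope on n independent rows, power comes from a noncentral t with n − 2 degrees of freedom and noncentrality

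0.3 × 2.370 × √n / 1 = 0.711 × √n.

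At n = 18 this is 0.711 × 4.243 = 3.017, and the power is 80.8%. At n = 17 it is 78.2%. So 18 is the smallest n that reaches 80%, and the stated figure reproduces.

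**2. What the 18 counts.** It is set against 30 participants, so the unit is the patient. If 18 patients each gave 8 independent contact rows (the protocol, Item 13, gives 8 contacts), there would be 18 × 8 = 144 rows, and the slope detectable with 80% power would be about 0.10, not 0.3. The calculation therefore fits one independent row per patient. This is an inference; the SAP does not state it.

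**3. What an unsplit slope picks up.** The documents give neither the between-patient share of variance nor any between- or within-patient correlation, so these are assumed. Setting A: 30 patients × 8 contacts; threshold and window each √0.5 × patient part + √0.5 × contact part; patient parts correlated 0.5 or 0.7; contact parts uncorrelated, so the true within-patient association is zero. The table gives the percentage rejecting at two-sided 0.05. Ranges cover repeated simulation runs; the random-intercept range covers both correlations.

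| Analysis | Correlation 0.5 | Correlation 0.7 |
|---|---|---|
| Random intercept, threshold not centred | 14–28 (both columns) | |
| One contact per patient | 25 | 48–49 |
| Patient means | 70–71 | 97 |
| Contacts pooled, no clustering | 87–88 | 98–99 |
| Within-patient (centred) slope | 4–6 | 4–6 |

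With zero between-patient correlation as well, pooling contacts still rejects 24–25%, because rows from one patient are treated as independent.

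**4. A second set of assumptions.** Setting B: 30 patients × 8 contacts, the SAP's predictor SD of 2.370 and total residual variance 1, between-patient slope 0.3, within-patient slope 0, and a between-patient share of 0.3 to 0.7. The chance of a significant positive slope is 19–27% with an uncentred random intercept, 19–68% with one contact per patient, 76–92% with patient means and 79–99% with pooled contacts. The centred slope gives about 3%, against a nominal 2.5% in that direction.

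**5. The reverse case.** With a within-patient slope of 0.3 and a between-patient slope of 0, the patient-mean regression succeeds in only 3–13% of runs, against about 100% for the centred model.

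**The case against.** The best defence is that this is a gap in description, not a wrong analysis. Much of it stands.

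- The window is a response elsewhere: in the SA1.1 mixed model, and in the secondary analysis that regresses the primary outcomes on EEG and then on ECoG. A reader might infer that the SAP nowhere models the window with repeated measures; that is not so. Neither of these, however, is a within-patient model of window on ERP threshold.
- A reader might also infer that the SAP specifies one row per patient, or an analysis of patient means. It does neither. A simple-regression sample size can be a planning simplification, and the reference to a given contact may mean contact-level rows. The method named for SA1 is Proc Mixed, so the random-intercept figures (14–28%) are closer to what might be done than the 70–99%. They still exceed 5%. If a separate regression per contact is meant, that is again one row per patient.
- It is tempting to say that EEG and ECoG will be judged by comparing slopes. The wording on linear contrasts allows that reading but does not require it, and an R-square increment is already planned as secondary. That increment has no within-patient split either.
- Milestone 2.5 looks for changes within individuals, so the protocol does not endorse a between-patient result. It sets no formal test.
- SA1.2 is not the only evidence on ERP-guided selection. SA2.1 and SA2.2 contrast the selection strategies acutely, and SA2.3 does so in the randomized crossover. Contacts are ranked inside each patient (Milestone 2.6), not chosen from a group-level SA1.2 p-value.

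**Conclusion.** The point holds as a mismatch between estimand and model. The SA1.2 question is within-participant; the mixed model written for it holds no clinical outcome; and the powered regression has neither a patient effect nor a within/between split. The stated sample size is arithmetically right for what it tests, but that is not the within-patient slope.

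The size of the problem cannot be read from the documents. It depends on the row structure finally used, on the between-patient share of variance and on the between-patient correlation, all assumed here. Under those assumptions the rate of false within-patient claims runs from about 14% to 99%, against about 5% for the within-patient slope. The documents do not support the stronger conclusion that SA1.2 will be declared positive on between-patient information: they leave that open, and the milestone wording points the other way. Because SA2.1 to SA2.3 also test ERP-guided selection, this is a should-fix.

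**What to change.** 1. State the SA1.2 primary model: therapeutic window per contact as response; the contact's ERP threshold entered as two terms, the patient's mean and the deviation from that mean; and a random patient intercept. Make the coefficient of the deviation the primary test.
2. First state how ERP responses become a value per contact. The protocol (Item 16a, Intraoperative ERP assay) elicits them only from neighbouring contact pairs, at 0 to 5 mA in 1 mA steps. If no mapping is defined, define both window and threshold per stimulation pair.
3. Keep the model with ERP measures as response, labelled descriptive.
4. Apply the same within-patient split to the planned R-square comparison of EEG and ECoG.
5. Restate the SA1 power for the within-patient slope, giving the assumed number of contacts per patient and the variance split.

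The cost is SAP wording and one re-run power statement. No new data or visits are needed.

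### The SA1.2 contrast of EEG and ECoG regression coefficients on thresholds in mA mixes predictive strength with threshold spread and should be replaced by a scale-free comparison of prediction.

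*SAP*

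**What the plan says.** The SA1 paragraph of the SAP sets out the direct comparison of the two recording modalities: "Using linear contrasts from the regressions, we will directly compare whether EEG and ECOG measures of DBS amplitude thresholds", one threshold for a change in P1/N1 latency and one for the appearance of the HFO, "better predict the size of the therapeutic window for a given DBS electrode contact". No model equation is given. No standardisation of the thresholds is stated, and no test on correlation, R-square or prediction error is named for this comparison.

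The sample-size text in the same paragraph puts the predictor in mA: "the standard deviation of the predictor variable, DBS amplitude threshold, is 2.370 mA". It gives one SD, not one per modality.

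A further analysis, labelled secondary, regresses the outcomes on EEG first and then asks how much of the remaining variance ECoG explains. Its power is stated in terms of R-square. Directly after it comes the decision rule: "If we cannot demonstrate superiority of ECOG, we would default to the less invasive modality".

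**The concern.** A linear contrast is a linear combination of model coefficients. A coefficient on a threshold in mA says how far the therapeutic window moves per mA. It does not say how closely the window follows the threshold. Suppose ECoG thresholds fall in a narrower mA range than EEG thresholds but track the window equally well. The ECoG coefficient is then steeper, and the contrast can report a difference in prediction that does not exist. The reverse can also happen: equal coefficients can conceal a large difference in predictive value.

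At stake is the SAP's only stated head-to-head answer to which modality predicts better. ECoG needs a subdural strip and EEG does not, so readers will give that answer weight.

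**Working it through.** **1. The unit of the predictor.** Inputs from the sample-size text for SA1:
- slope: "an alternative regression slope of 0.3 or higher standardized units"
- predictor SD: 2.370 mA
- residual SD: "the standard deviation of the normalized residuals ($sd=1$) of the therapeutic window"
- test: "using a t-test with a 0.05 two-sided significance level"
- claim: "a sample size of 18 will have 80% power to detect a difference between a null hypothesis regression slope of 0"

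For a simple regression slope the noncentrality is slope × SD(threshold) × √n / SD(residual) = 0.3 × 2.370 × √18 / 1 = 3.02, on 16 df. Power is 80.8%, so the stated 80% reproduces with 0.3 read as a slope per mA. With a predictor of SD 1, N = 18 gives 22% power, and 80% would need N = 90. The plan's own regression is therefore on the mA scale, and its standardised units can apply only to the window.

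**2. What the contrast tests.** Let T be the threshold, W the window, r their correlation, and ρ the correlation between EEG and ECoG thresholds.
- Separate regressions: slope = r × SD(W) / SD(T). SD(W) is common to both, so equal slopes means r_EEG / SD_EEG = r_ECoG / SD_ECoG.
- One joint regression: the EEG coefficient is [SD(W) / SD_EEG] × (r_EEG − ρ r_ECoG) / (1 − ρ²), and likewise for ECoG. If both correlations equal r, this becomes [SD(W) / SD_EEG] × r / (1 + ρ).

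Under equal prediction, then, both forms of the contrast are zero only if the two SDs are equal.

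**3. A missed difference.** The plan's figures imply R-square = (0.3 × 2.370)² / [(0.3 × 2.370)² + 1] = 0.5055 / 1.5055 = 0.336. Give both modalities a slope of 0.3 per mA, but let one have half the spread (1.185 mA, assumed). Its R-square is (0.3 × 1.185)² / 1.5055 = 0.084. That is a fourfold difference in R-square with a separate-slopes contrast of exactly zero.

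**4. False differences.** The simulation assumes 30 independent observations, normal data, R-square 0.336 for both modalities (r = 0.58) and ρ from 0.5 to 0.7. The correlation and the SD ratios are assumptions; the documents give neither. Separate slopes were compared with a standard error that allows for the shared observations. The table shows rejection at a nominal 5%.

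| SD ratio | Separate regressions | Joint regression | Joint, standardised thresholds | Williams' test of dependent correlations |
|---|---|---|---|---|
| 1 | about 5% | about 5% | 5-6% | about 5% |
| 0.75 | 20-24% | 6-7% | 5-6% | about 5% |
| 0.5 | 58-67% | 9-14% | 5-6% | about 5% |

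**5. Sensitivity.** With R-square between 0.25 and 0.50 and ρ of 0.5 or 0.8, a twofold SD ratio gives 45-91% for separate slopes and 6-27% for the joint contrast. With 240 observations (30 × 8 contacts, clustering ignored), R-square 0.336 and ratios from 1.25 to 2, the ranges are 67-100% and 7-73%. Williams' test stays near 5% throughout.

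**The case against.** The strongest reply is that the SAP already contains a scale-free comparison. Incremental R-square does not change when mA are rescaled, and the rule on falling back to the less invasive modality comes straight after it. A reader might infer that the coefficient contrast decides whether the invasive recording is needed. The documents do not support that. The rule is placed with the R-square analysis, Milestone 2.6 of the protocol fixes the EEG criteria for contact selection in advance, and the protocol's section on minimising risks says the assay results do not change surgical decisions. This stands and limits the consequence. It does not repair the contrast: the R-square analysis is secondary and runs one way only, asking what ECoG adds once EEG is in the model.

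Second, the SAP never says slopes and gives no equation. The regressions it refers to could be the mixed models described just before, and the mA scale is inferred from a power calculation for a single slope. This also stands, so the point depends on a reading. But the possible readings have very different error rates, which is itself a reason to specify the model.

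Third, EEG and ECoG are recorded simultaneously on the same stimulation grid, so their spreads may be similar. If both measured one underlying threshold with only additive noise, the noisier modality would have both a flatter slope and a lower correlation, and equal prediction would imply equal spread. That is correct: a false difference needs one modality's thresholds to be compressed or stretched relative to the other's at equal predictive strength. The plan neither rules this out nor checks for it.

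That the two predictors are correlated is not a flaw in itself, since a joint model uses their covariance.

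**Conclusion.** The concern holds in a limited form. Read as a contrast of coefficients on mA thresholds, the SA1.2 comparison does not isolate which modality predicts better. Its error is large with separate regressions and a twofold difference in spread (58-67%), small to moderate in a joint model (9-14% at the same ratio), and absent if the spreads are equal.

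Two stronger readings should be resisted. One is that the contrast tests scale instead of prediction. It tests correlation divided by SD, a mix of both, and is a pure test of scale only when the correlations are already equal. The other is that false-difference rates above one half are to be expected in this trial. Those rates need separate regressions and SD ratios that the documents do not give.

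The simulated rates treat observations as independent, whereas contacts are clustered within patients. They show direction and rough size and do not forecast this trial's error rate. The change is worth making because it uses the same data and costs little.

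**What to change.** - Write out the SA1.2 model and replace the coefficient contrast with a scale-free comparison on the same contacts. Use either the difference in leave-one-patient-out R-square or prediction error between the EEG and ECoG models, or the difference between the two dependent correlations with therapeutic window. These are alternatives and answer slightly different questions, so choose one in advance.
- Take the confidence interval from a bootstrap that resamples patients, so that clustering of contacts is respected.
- Do this separately for the latency threshold and the HFO threshold.
- At the very least, contrast coefficients on thresholds standardised across the whole sample. Do not standardise within patient: it discards between-patient information and fails where a patient's thresholds are all equal.
- State that the modality default rests on the incremental R-square analysis.

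The cost is SAP wording and a little programming, with no new data. Intervals will be somewhat wide at n = 30.
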